| | 13.3 | Vital sign assessments - abnormal | |
| , C | 13.4 | Electrocardiogram (ECG) – abnormal | |

LIST OF ABBREVIATIONS

Analysis Set
Informed consent form
International League Against Epilepsy
Lacosamide
Lever function test
ledical Dictionary for Regul
eferred term
ious adve
: Adverse event(s) AE(s) AED(s) **ALT AST**

CRF ECG(s)

eCRF

EEG FAS

ICF

ILAE

LCM

LFT

MedDRA

РТ

SAE(s)

QT interval corrected using Bazett's formula QTcB QT interval corrected using Fridericia's formula QTcF QT interval corrected using the population **QTcP**

Statistical analysis plan SAP Standard deviation SD This document cannot be used to support amy System organ class SOC

Safety Set

Treatment-emergent adverse event

Upper limit of normal

World Health Organization Drug Dictionary

Confidential Page 5 of 35

INTRODUCTION

This Statistical Analysis Plan (SAP) describes the statistical principals that are applied for the This SAP should be read in conjunction with the following documents that provide all necessary background information and rationale for the current study and its design.

1) Finalized Study Protocol Amendment

2) Electronic Case P.

Lessa vertensions of val

2 PROTOCOL SUMMARY

2.1 Study objectives

2.1.1 **Primary objectives**

The primary objectives of this study are the following:

- To evaluate the safety and tolerability of long-term administration of lacosamide (LCM) at doses up to 400mg/day in Japanese and Chinese adults with epilepsy who have completed the Treatment and Transition Period of EP0008
- To allow subjects who had completed the Treatment and Transition Periods of EP0008 to receive LCM

2.1.2 Secondary objective

The secondary objective of this study is the following:

- To evaluate the efficacy of long-term administration of LCM at doses up to 400mg/day in Japanese and Chinese adults with epilepsy who have completed the Treatment and Transition Periods of EP0008
- 2.2 Study variables
- Safety variables 2.2.1

Primary safety variables 2.2.1.1

The primary safety variables are the following:

Adverse events (AEs) reported spontaneously by the subject or observed by the investigator

Page 6 of 35

Subject withdrawals due to AEs

2.2.1.2 Other safety variables

The other safety variables are the following:

- Changes in hematology, clinical chemistry, and urinalysis parameters
- Changes in 12-lead electrocardiograms (ECGs)
- Changes in vital sign measurements (ie, blood pressure, pulse rate)

Changes in body weight

2.2.2 **Efficacy variables**

2.2.2.1 Primary efficacy variables

No primary efficacy variables are defined for EP0009.

2.2.2.2 Secondary efficacy variables

The secondary efficacy variables are the following:

- Percent change from Baseline in partial-onset seizure frequency per 28 days, where Baseline is defined as the Baseline Period of EP0008
- 50% response, where a responder is a subject experiencing a \geq 50% reduction from Baseline in partial-onset seizure frequency per 28 days, and Baseline is defined as the Baseline Period of EP0008

2.2.2.3

Other efficacy variables are the following:

- Other efficacy variables
 ner efficacy variables are the following:
 75% response, where a responder is a subject experiencing a ≥75% reduction from Baseline in partial-onset seizure frequency per 28 days and Baseline is defined as the Baseline Period of EP0008
- Subjects who achieved "seizure-free" status (yes/no)
- Percentage of seizure-free days
- Subjects who are changed to LCM monotherapy for at least 6 months
- Subjects who are changed to LCM monotherapy for at least 12 months

Study design and conduct 2.3

EP0009 is a Phase 3, multicenter, open-label, uncontrolled, extension study designed to evaluate the safety, tolerability, and efficacy of long-term administration of LCM as adjunctive therapy at doses up to 400mg/day in Japanese and Chinese adults with partial-onset seizures with or without secondary generalization who have completed the Treatment and Transition Periods of EP0008 and chose to enroll in EP0009.

Visit 1 of EP0009 is the same as the Final Visit of EP0008. Visits 2 through 4 of EP0009 will occur at 4-week intervals relative to the date of Visit 1. Beginning with Visit 5, each visit will occur at 12-week intervals relative to the date of Visit 1 until the End-of-Study/Withdrawal Visit.

At the completion of EP0008, all subjects who choose to enroll in EP0009 will be taking a dose of LCM 200mg/day. During the EP0009 Treatment Period, the investigator will be allowed to increase or decrease the doses of LCM and/or up to 3 concomitant antiepileptic drug(s) (AED[s]) to optimize tolerability and seizure reduction for each subject. The LCM dose may be decreased to 100mg/day or increased, no faster than 100mg/day per week, up to 400mg/day. Changes in concomitant AED(s) will be allowed only if the LCM dose has been stable for the previous 4 weeks; LCM dose must remain stable during changes to concomitant AED(s). Subjects may take no more than 3 concomitant AEDs except when temporary (≤12 weeks) use of an additional AED is required to switch to a new AED (ie, taper from old AED during titration of a new

Confidential Page 7 of 35 **UCB** 12Sep2014 Statistical Analysis Plan Lacosamide EP0009

AED). New AED(s) may be added only when the subject has not optimally or adequately responded to a maximum tolerated dose of LCM. The concomitant AED(s) can be carefully tapered or discontinued at the discretion of the investigator. Monotherapy with LCM is permitted. Increasing the dose of LCM and/or concomitant AED(s), as well as the addition of a new AED, should be done at a visit (scheduled or unscheduled).

At the end of the Treatment Period, an End-of-Study Visit will be required. If subjects prematurely withdraw from the study, a Withdrawal Visit will be required. Subjects who complete the Treatment Period and choose not to continue on to commercial LCM treatment, and subjects who prematurely withdraw from the study, will enter a Taper Period. During the Taper Period, subjects receiving doses greater than LCM 200mg/day at the End-of-Study/Withdrawal Visit should be tapered off gradually at a recommended decrease rate of LCM 200mg/day per week, unless the investigator feels that safety concerns require more rapid withdrawal of LCM. UCB (or designee) should be contacted if a more rapid withdrawal is required. A slower taper (e.g., LCM 100mg/day per week) is permitted, if medically necessary. Subjects receiving doses of LCM 200mg/day or lower at the End-of-Study/Withdrawal Visit are not required to taper off LCM. A Final Visit will be required 2 weeks after final LCM dose. Subjects who complete the Treatment Period and choose to continue on to commercial LCM treatment are not required to enter the Taper Period to taper off LCM or to return for a Final Visit; the End-of-Study Visit will be the last visit for these subjects. If LCM is not commercially available in a subject's country at the time the study closes, access to LCM will be provided according to local laws.

At selected sites, Japanese subjects may participate in an additional study (EP0024) with the intravenous formulation of LCM without withdrawing from EP0009. The study period of EP0024 will be included in that of EP0009. Subjects will continue to receive their current dose of LCM at the time of entry and remain stable for the duration of EP0024. Subjects who complete or withdraw from EP0024 will be given the opportunity to resume their participation in EP0009 with oral LCM treatment. In the event that a subject withdraws from EP0024 and is required to taper off LCM, the subject will return to EP0009 and taper using LCM tablets. Adverse events and concomitant treatment(s)/medication(s) that occur or were administered during EP0024 will be recorded in EP0024. Ongoing AEs and concomitant medication(s)/medical procedure(s) originating from the EP0024 will be followed in EP0009 until resolution or until stable. Where possible, data updates related to the resolution of ongoing AEs and concomitant medication(s)/medical procedure(s) from EP0024 will be reported in the EP0024 database (eg, updates are made in the EP0024 databases until the database is locked). All other data reported for EP0024 will be captured in the EP0024 database. Per the EP0024 protocol, the study (EP0024) will require hospitalization. Hospitalization for study participation does not need to be reported as an SAE.

Determination of sample size

No formal sample size determination has been performed because EP0009 is an extension study. Approximately 378 subjects, ie, 70% of subjects who were randomized in EP0008, are anticipated to participate in this extension study.

Confidential Page 8 of 35

3 DATA ANALYSIS CONSIDERATIONS

3.1 General presentation of summaries and analyses

Datasets will be analyzed using SAS version 9.1.3 or higher. All tables and listings will use Courier New font size 9.

Descriptive statistics will be displayed to provide an overview of the safety and efficacy results.

For categorical parameters, the number and percentages of subjects in each category will be presented at the relevant time point. The denominator for percentages will be based on the number of subjects appropriate for the purpose of analysis. Percentages will be presented to one decimal place. Percentages will not be presented for zero counts and 100% will be presented as an integer.

For continuous parameters, descriptive statistics will include number of the subjects, mean, standard deviation (SD), median, minimum, and maximum. The minimum and maximum will be reported to the same number of decimal places as the raw data recorded in the CRF. The mean, SD, median will be reported to one more decimal place, than the raw data recorded in the CRF. In general, the maximum number of decimal places reported should be 4 for any summary statistics.

Subjects who withdraw early from the study will be evaluated based on the data collected at each visit attended or period entered. Data summaries will be presented overall and by randomized dose in EP0008 unless otherwise specified. Additionally, summaries will be presented separately by country.

3.2 General study level definition

3.2.1 Relative day

Relative day is defined as the day relative to the first dose in EP0009 of LCM.

- If the start date of an event occurred prior to the first dose of LCM in EP0009, the relative day is calculated as start date minus first LCM dose date. In subject data listings, relative days based on this situation will be preceded by a "-".
- If the start date of an event occurred on or after the first dose of LCM but prior to or on the last dose of LCM in EP0009, the relative day is calculated as start date minus first LCM dose date + 1.
- If the start date of an event occurred after the date of last dose of LCM in EP0009, the relative day is calculated as start date minus last dose date. In subject data listings, relative days based on this situation will be preceded by a "+".

For quantitative ECGs, Baseline was defined as the average of the 3 ECG measurements taken at Visit 3 of EP0008. If a subject had less than 3 ECG measurements on the day of Visit 3 of EP0008, Baseline was to be defined as the average of the available ECGs on the day of Visit 3 of EP0008. If no ECGs were available on the day of Visit 3 of EP0008, Baseline was not defined for ECG assessments.

For laboratory and vital sign data, Baseline was the last non-missing evaluation prior to the first dose of intake of the study drug in EP0008.

Protocol deviations 3.4

The data will be reviewed to identify important protocol deviations. Important protocol deviations will be identified and documented prior to database snapshot for interim reports and database lock for the final analysis based on predefined criteria. Important deviations will be categorized as follows:

- Inclusion criteria
- Exclusion criteria
- Withdrawal criteria
- Prohibited medications
- Procedure non-compliance

12Sep2014 EP0009

Other

A list of subjects with important protocol deviations will be agreed upon and documented prior to database lock.

All subjects Screened
All subjects screened will consist of all subjects who signed the informed consent form (ICF);

3.5.2 Safety Set

The Safety Set (SS) will include all enrolled and in EP0009.

3.5.3 **Full Analysis Set**

The analysis set for the efficacy variables will be the Full Analysis Set (FAS) and will include all subjects in the SS having at least 1 day with available seizure diary data in EP0009.

Treatment assignment and treatment group 3.6

All subjects treated in EP0009 received LCM at doses ranging between 100mg/day to 400mg/day. A subject's LCM dose may be decreased to 100mg/day or increased, no faster than 100mg/day per week, up to 400mg/day. In terms of results presentation, summaries will present subjects overall and by randomized dose in EP0008: placebo, LCM 200mg/day, or LCM 400mg/day, unless otherwise specified.

Center pooling strategy 3.7

For the purpose of the summaries and analyses, the term 'Center' will be used to define each site.

All centers will be pooled by country for the purpose of analysis.

Descriptive summaries will not be presented by individual center. Subject data listing will provide data sorted by country and individual center.

3.8 Coding dictionaries

All AEs will be coded using the Medical Dictionary for Regulatory Activities (MedDRA) version 16.1.

All medications will be coded using the World Health Organization Drug Dictionary (WHO-DD) version SEP/2013.

All coding will be performed prior to database lock.

STATISTICAL/ANALYTICAL ISSUES

Adjustments for covariates

This section is not applicable.

Handling of dropouts or missing data

For by-visit analyses, data from the Withdrawal Visit will be presented with data corresponding to the next scheduled visit for the subject.

Confidential Page 11 of 35 Due to the potential for missing number of seizures for a given diary date, seizure frequency will be calculated using only the number of days for which seizure data is provided.

For analyses of treatment-emergent AEs (TEAEs) and concomitant medications, a complete date must be established in order to correctly identify the TEAE or medication as occurring during treatment or not. For purposes of imputing missing components of partially reported start and stop dates for adverse events and for medications, the algorithms listed below will be followed. Start and stop dates of AEs or concomitant medication will be displayed as reported in the subject data listings (ie, no imputed values will be displayed in data listing).

• Missing start day, but month and year present: If the start data of the start data of the same month and year present.

- Missing start day, but month and year present: If the start date of study treatment occurred in the same month and year as the occurrence of the event/medication, the start day of the event/concomitant medication will be assigned to the day of first intake of study treatment in order to treat the adverse event and medication as treatment-emergent and concomitant, respectively. Otherwise the start day will be set to the 1st day of the month.
- Missing start day and month, but year present: If the start date of trial medication occurred in the same year as the occurrence of the event/medication, the start day and month will be assigned to the date of first intake of study treatment in order to treat the adverse event and medication as treatment-emergent and concomitant, respectively. Otherwise the start day and month will be set to January 1st.
- Start date is completely unknown: The start date of the event/concomitant medication will be assigned to the date of first intake of study treatment.
- Missing end day, but month and year present: The end day will be set to the last day of the month.
- Missing end day and month, but year present: The end day and month will be set to the maximum of the date of study or the date equivalent to 30 days after last intake of study treatment.
- End date is completely unknown: The end date will not be imputed.

However, if the study termination year and year for the date which is 30 days after last intake of study treatment are greater than the event/concomitant medication year, the day and month are to be set to December 31st.

Relative day is not calculated for partial dates in cases where relative day is shown in a subject listing. In such cases, relative day should be left blank in the subject data listings.

Subjects participating in EP0024 while also enrolled in EP0009 will have missing data for seizure frequency and drug dosing while participating in the EP0024 trial. As the duration of the EP0024 study will be short (3-7 days), no imputation for data missing due to participation in EP0024 will be performed. Subjects will be assigned the same dose in EP0024 as that assigned in EP0009 for the two weeks prior to the start of EP0024. As such, time during the EP0024 study will not be subtracted from the exposure calculations (eg, exposure will be from the start of LCM treatment in the EP0009 study until the date of last dose of LCM in EP0009).

For the calculation of variables related to seizure frequency, the dates during participation in EP0024 will be considered as not done for the purpose of efficacy analyses for trial EP0009 (eg, these dates will not be considered as days evaluated for seizure frequency). Due to the short nature of the EP0024 study, only a few days of seizure frequency data are expected to be missing

due to participation in EP0024 unless otherwise specified (eg, for the evaluation of seizure freedom).

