6.3 Medical history and concomitant disease

Medical history and concomitant diseases will be as reported as of Visit 1 of EP0008.

Concomitant diseases are medical history events which were ongoing at Visit 1 of EP0008.

Summary tables of medical history and concomitant diseases will be provided for the SS as follows:

- A summary of medical history by MedDRA system organ class (SOC) and preferred term (PT) will be presented overall, by EP0008 randomized treatment group, and country separately.
- A summary of concomitant disease by MedDRA system organ class (SOC) and preferred term (PT) will be presented overall, by EP0008 randomized treatment group, and country separately.
- A by-subject listing of medical history.
- A by-subject listing of concomitant diseases.
- A by-subject listing of procedure history.

Concomitant medications

Concomitant medications will be defined as any medications taken concurrent with LCM if the start date was prior to the first dose with ongoing status, or the start date was on or after the date of first dose of study drug in EP0009. Medications with a missing start date, whose stop date is either unknown or after the date of the first dose of study drug, will be considered concomitant.

Summary tables will be provided for the SS and FAS as follows:

A summary of concomitant medications (excluding AEDs) taken during Treatment Period will be provided by level 1 and level 2 ATC code. The tables will be presented overall, by EP0008 randomized treatment group, and by country separately.

- A summary of concomitant AEDs taken during the Treatment Period will be provided by Level 4 ATC code and preferred medication name. The tables will be presented overall, by EP0008 randomized treatment group, and by country separately.
- A by-subject listing of concomitant AEDs (Analysis population: SS)
- A by-subject listing of concomitant medications (non-AEDs) (Analysis population: SS)

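### SAP Section 4.2 sets some unknown or partial start dates to first intake without checking the stop date, so a record that ended before EP0009 dosing can start after it stopped

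*SAP*

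**What the plan says.** SAP Section 4.2 (Handling of dropouts or missing data) gives three start-date rules for adverse events and medications:

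- **Day missing, month and year the same as first intake:** "the start day of the event/concomitant medication will be assigned to the day of first intake of study treatment". If they differ: "Otherwise the start day will be set to the 1st day of the month".
- **Day and month missing, year the same as first intake:** "the start day and month will be assigned to the date of first intake of study treatment". If it differs: "Otherwise the start day and month will be set to January 1st".
- **Nothing known:** "The start date of the event/concomitant medication will be assigned to the date of first intake of study treatment", with no condition.

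The stated purpose of the first two is "in order to treat the adverse event and medication as treatment-emergent and concomitant, respectively". The end-date rules in the same section only fill in missing end components, for example "Missing end day, but month and year present: The end day will be set to the last day of the month". They do not compare the end with the start. Listings show dates as reported, so imputed dates act only on derived data and summary tables.

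SAP Section 6.4 (Concomitant medications) defines the medication class separately. It asks for use at the same time as LCM, with either a start before first dose and use continuing, or a start no earlier than the first EP0009 dose. It then adds a sentence that counts as concomitant "Medications with a missing start date, whose stop date is either unknown or after the date of the first dose of study drug".

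SAP Section 8.2 tabulates TEAEs by onset during the Treatment Period, which Section 3.2.2 begins at the first EP0009 dose.

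**The concern.** Section 4.2 wants complete dates so that each record can be placed correctly on or off treatment. When the start is uncertain but the stop is known to precede first EP0009 intake, the stop settles the question: the record was over before dosing. The rule ignores that information and places the start inside the Treatment Period.

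Two things are at stake. Adverse events are a primary safety variable (Section 2.2.1.1), and the onset date alone puts an event in the Section 8.2 tables. For medications, Sections 4.2 and 6.4 can give different classes to the same record, so two programmers following the SAP could produce different tables.

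The setting makes such records plausible. EP0009 Visit 1 is the EP0008 Final Visit (Section 2.3), so events and drugs that ended shortly before first EP0009 intake may exist.

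**Working it through.** The SAP gives no figure to reproduce. The check applies its rules as written to illustrative dates. **Assumption:** first EP0009 intake on 15 Jun 2013; this date and the record dates below are not in the SAP.

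**Step 1. Do starts fall after stops?**

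| Reported start | Reported stop | Start under 4.2 | Start after stop? |
|---|---|---|---|
| unknown | 5 Jun 2013 | 15 Jun 2013 | yes, by 15 − 5 = 10 days |
| 2013 | 10 Feb 2013 | 15 Jun 2013 | yes, by 18 + 31 + 30 + 31 + 15 = 125 days |
| Jun 2013 | 5 Jun 2013 | 15 Jun 2013 | yes, by 10 days |
| May 2013 | 5 Jun 2013 | 1 May 2013 | no |
| 2012 | 10 Feb 2013 | 1 Jan 2012 | no |
| unknown | 25 Jun 2013 | 15 Jun 2013 | no |

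All three rules can reverse the dates. A partial start does so only when its month and year, or its year, match first intake. The fourth and fifth rows are unaffected.

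**Step 2. Adverse events.** In the first three rows the imputed onset equals the first day of the Treatment Period. Read as an adverse event, each would be counted in Section 8.2 although it resolved before dosing. No SAP section adds a stop-date condition for events.

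**Step 3. Medications with a completely missing start.** The imputed start equals first dose, which satisfies the start-date part of the Section 6.4 definition. The missing-start sentence in 6.4 admits the record only if the stop is unknown or after first dose. Take known stop dates from 60 days before to 60 days after first intake:

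- dates tested: 60 + 1 + 60 = 121
- start after stop: 60, every stop before first intake
- class by imputed start differs from class by the missing-start sentence: 60 + 1 = 61

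The extra date is a stop on the day of first intake: 6.4 requires the stop to be after that day, while the imputed start already qualifies.

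**Step 4. Medications with a partial start.** The missing-start sentence does not clearly reach these. They are kept out, if at all, by the general requirement that the drug be used alongside LCM.

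**Step 5. After the change.** If first intake is assigned only when the stop is unknown or after first intake, which is the 6.4 condition, no start falls after its stop and the two sections agree on all 121 dates. If 4.2 instead says not before first intake, the 60 reversals also go. The same-day stop then remains the one disagreement (61 − 60 = 1) until 6.4 is worded to match.

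**The case against.** **Moving uncertain starts into the treatment period is deliberate and conservative.** The SAP states that aim for matching partial dates, and it is reasonable where timing is unresolved. It does not cover a record whose reported stop resolves the timing.

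**Section 6.4 already protects medications.** This largely stands. 6.4 is the more specific section, requires use alongside LCM, and has a stop-date condition for missing starts. A reader might infer that an AED with a year-only start and a stop before first dose is bound to be tabulated as concomitant. The documents do not support that: such a drug was not used alongside LCM, whatever start is imputed. The explicit clash is confined to completely missing starts.

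**Monotherapy.** A reader might also infer that the counts in Section 9.3.4 are distorted. Nothing in the SAP shows this. An interval whose stop precedes first intake covers no later treatment day, so it cannot interrupt a later run of 6 or 12 months.

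**Adverse events.** A miscount requires that an event resolved before EP0009 dosing be present in the EP0009 data. The SAP does not say such events are carried over, so the exposure is possible but not established.

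**Which first intake?** Section 4.2 does not name the study. EP0009 is the natural reading, given Sections 3.2.1, 3.2.2 and 6.4. If EP0008 intake were meant, the conflict with 6.4 would largely disappear, but a start could still fall after its stop.

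**Conclusion.** The point holds as a minor drafting error. Section 4.2 can place a start after a known stop for a completely unknown start, and for a partial start that matches first intake. It does not do so for partial starts in general. For adverse events there is no correcting rule. For medications with a completely missing start, the imputed date and the missing-start sentence in 6.4 lead to opposite classes. For partial starts, the conflict rests only on the requirement of concurrent use.

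The conclusion assumes that first intake means first EP0009 intake and, for TEAEs, that events resolved before that date appear in the EP0009 data. The number of affected records cannot be derived from the SAP and is probably small. It would be too strong to say that every affected record is certainly misclassified: for medications, 6.4 can still exclude it. Displayed dates in listings are not affected.

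**What to change.** In Section 4.2, apply the end-date rules first and then add one condition to all three start-date rules:

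- Name the reference date as first intake in EP0009.
- Assign it, where the rule now does so, only if the stop date, reported or imputed, is missing or not before first EP0009 intake.
- If the stop is before first EP0009 intake, do not class the record as treatment-emergent or concomitant. For a partial start, impute the earliest date that fits the reported parts and is not later than the stop. For a completely unknown start there are no reported parts to use, so leave the start missing or set it to the stop date.

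In Section 6.4, cross-refer to this rule and use the same boundary for a stop on the day of first intake. Either 6.4 accepts a same-day stop or 4.2 requires a later one.

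Under the illustrative dates, the year-only start with stop 10 Feb 2013 becomes 1 Jan 2013, and the June start with stop 5 Jun 2013 becomes 1 Jun 2013. Neither is counted as on treatment. A stop given only as June 2013 becomes 30 Jun 2013 under the existing end-date rule, so a record whose timing is truly unresolved still counts as on treatment.

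The cost is a short SAP edit and one programming condition, with no change to data collection. Section 4.3 repeats all analyses at each interim report, so one correction serves them all.
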